**Intervention Group (Pharmacist Interventions):**

Participants enrolled in the intervention group will receive pharmacist interventions, in addition to standard care outlined in the Alberta College of Pharmacist Standards of Practice for Pharmacist and Pharmacy technicians (9).

Unique pharmacist interventions will include the following (in person) at enrolment (month 0) and at the scheduled month 1, 3, and 6 in-person or telehealth pharmacist meetings:

**1) Patient Assessment:**

- Recording participant scores from the combined PHQ-9/GAD-7 questionnaire tool (Appendix 4) completed by the participant, which includes:
  - PHQ-9 (Patient Health Questionnaire 9-item), a multipurpose instrument for screening, diagnosing, monitoring and measuring the severity of depression
  - GAD-7 (Generalised Anxiety Disorder 7-item)
- If determined clinically relevant by the pharmacist partner will assess:
  - appearance, current mood, sleeping patterns, mental health, medical history, social history, family history, relationships with others, suicidal ideation, previous suicide attempts or hospitalizations, current employment status.

2) Pharmacist-initiated prescribing dose adjustment, medication change to different medication, deprescribing, or prescribing adjunctive add-on medication, to achieve clinical response and/or remission of MDD and/or GAD and establish appropriate cognitive/functional status as per CAMAT guidelines (7, 8).

3) Provide regular communication updates with the patient's family physician after each contact with the patient (via fax or electronic charting).

4) Providing medication counselling and educational support to the participant.

5) Identification of adverse drug effects, drug interactions, or severe deterioration (i.e. suicide attempt)

6) Interim telephone/telehealth follow-up conducted by the pharmacist partner since the last in-person follow-up & a minimum of 1-2 weeks after the last in-person follow-up that involved a dose adjustment, prescribing of adjunctive medication, or discontinuation of therapy. (Note: a telephone follow-up does not replace the scheduled in-person/telehealth follow-up).

7) Collaborate with physician to arrange referral to psychologist, psychiatrist, counsellor or social worker for psychotherapy

Should the participant from the interventional group drop out or complete the 6 month study period, they will be offered to continue with similar interventional care or standard pharmacist care but no data will be collected since their dropout or following study completion.

**Control Group (Standard Pharmacist Care):**

Patients randomised to the standard pharmacist care groups will receive:

- Standard pharmacist care, as outlined in the Alberta College of Pharmacist Standards of Practice for Pharmacist and Pharmacy technicians (9), and physician care with no specific interventions for the duration of the 6 month study period.
- Should participants from the usual care group drop out or the participant completes the 6 month study period, they will be offered care similar to the interventional group or standard pharmacist care but no data will be collected since their dropout or following study completion.

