**Both Groups**

- Indication of medication (i.e. MDD, GAD, or both) will be recorded by the pharmacist partner in the secured study electronic website/database.
- The electronic PHQ-9/GAD-7 questionnaire (Appendix 4) will be sent securely to and completed by the participant at enrollment (month 0) and prior to the participant's in-person scheduled month 6 (final). The questionnaire results will be available to the study investigator and pharmacist participants but linked only to the participant's study ID.
- Participants will receive a pamphlet copy of Alberta Health Services Access Mental Health resource pamphlet "Know Your Addiction and Mental Health Options" which provides information regarding walk-in services, crisis support, and urgent care (10). An equivalent alternative pamphlet can be developed and provided by the study team if this document becomes obsolete or additional update/information is required.

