**Continuity of care plan:**

- Should participants from either group drop out or complete the 6 month study period, they will be offered care similar to the interventional group or standard pharmacist care as outlined in the Alberta college of pharmacists standards of practice but no data will be collected since their dropout or study completion.

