## **Outcomes:**

### **Primary outcomes:**

The primary outcome is the mean score difference in PHQ-9 and GAD-7 scores from baseline to end of study participation, between the intervention and standard pharmacist care groups.

- Both PHQ-9 and GAD-7 are validated tools for measuring major depressive disorder and generalised anxiety, respectively, in the primary care setting. They are brief and can be self-administered, with similar results yielded with health care provider administered reports. These are desirable given the time restraints and competing demands we anticipate for community pharmacist partners participating in the study(11, 12).
- PHQ-9 scores reflect depression severity; Ranges from 0-27 (Scores: 0-4 none/minimal, 5-9 mild, 10-14 moderate, 15-19 moderately severe, 20-27 severe) (13).
- GAD-7 scores reflect anxiety severity; Ranges from 0-21 (Scores: 0-4 none/minimal, 5-9 mild, 10-14 moderate, 15-21 severe) (13)

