#### **Analytical Plan:**

All analyses will be conducted on an intention to treat basis. In the case of missing data, a last observation carried forward approach will be used.

Primary outcome will be analysed using ANCOVA, adjusting for all covariates with  $p < 0.25$  between groups

Secondary outcomes will be analysed using ANCOVA, t-test or chi-square test where appropriate, adjusting for all covariates with  $p < 0.25$  between groups.

Trial and Data Management will be done by EPICORE Centre

---

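### Measurement stops at every dropout in both arms, so the intention-to-treat comparison rests on carried-forward scores and any crossover of controls to the tested care goes unrecorded

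*Protocol*

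**What the plan says.** Four parts of the Protocol bear on this.

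- **Dropout rule, control arm** (Control Group). Controls receive standard pharmacist care and "physician care with no specific interventions for the duration of the 6 month study period". If they drop out, "they will be offered care similar to the interventional group or standard pharmacist care but no data will be collected since their dropout".
- **Dropout rule, intervention arm** (Intervention Group, closing paragraph). Those who drop out "they will be offered to continue with similar interventional care or standard pharmacist care but no data will be collected since their dropout". The Continuity of care plan repeats the rule for both arms: "Should participants from either group drop out or complete the 6 month study period, they will be offered care similar to the interventional group", with standard care as the alternative and again no further data.
- **Analysis** (Analytical Plan). "All analyses will be conducted on an intention to treat basis", followed by "In the case of missing data, a last observation carried forward approach will be used".
- **Endpoint and schedule.** Under Primary outcomes, "The primary outcome is the mean score difference in PHQ-9 and GAD-7 scores from baseline to end of study participation". The Both Groups section fixes questionnaires at months 0 and 6 for everyone. The Intervention Group section adds recorded scores at months 1 and 3 in that arm only. The Randomization section sends each participant the group allocation together with an electronic questionnaire link, with completion alongside the pharmacist for those who cannot receive a link.

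**The concern.** An intention-to-treat comparison needs outcomes for everyone randomised, whatever care they went on to receive. Here the Protocol decides in advance not to collect them from anyone who drops out, including a person who only wants different care and would still answer a questionnaire. Drop out is not defined, so leaving the assigned care and withdrawing consent to data are treated alike.

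The rule also works differently in the two arms. An intervention leaver may keep care already being received. A control leaver is offered care that was withheld while in the study, and knows it was withheld. That could draw controls out, particularly those not improving, and their move to the tested care would leave no trace in the data.

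At stake is the primary comparison. If dropout differs by arm, part of the PHQ-9 and GAD-7 difference will reflect how leavers are scored. An endpoint tied to each person's end of participation also lets the time of measurement vary between participants. A statistical analysis plan can change how gaps are filled but cannot supply scores that were never collected.

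**Working it through.** **1. The plan's own figure.** Inputs from the Sample Size Calculation: PHQ-9 difference 4.3, SD 6.9, two-sided alpha 0.05, power 80%. The two-sample t calculation gives 41.4, hence 42 per arm (84 in total), with power 80.6%. Allowing for 10% loss, 42/0.9 = 46.7, hence 47 per arm. Both stated figures reproduce. The 10% protects the number measured; it gives no protection against bias.

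**2. Bias if leavers are scored at baseline.** These inputs are assumptions unless noted: no true effect; mean six-month fall m = 3 to 7 points; SD of change σ = 6.9 (borrowed from the Protocol's baseline SD); dropout d_I = 10% in the intervention arm and d_C = 20% or 30% in the control arm. The documents give only the single 10% figure. Let ρ be the correlation between improvement and staying in, and φ(z_d) the standard normal density at the d-quantile. Then

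arm mean = (1 − d)·m + ρ·σ·φ(z_d)

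bias = (d_C − d_I)·m + ρ·σ·[φ(z_I) − φ(z_C)]

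with φ(z) = 0.1755, 0.2800 and 0.3477 at 10%, 20% and 30%. A positive value favours the intervention.

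| | d_C = 20% | d_C = 30% |
|---|---|---|
| ρ = 0 (leaving unrelated to outcome) | 0.1m = +0.3 to +0.7 | 0.2m = +0.6 to +1.4 |
| ρ = 0.5 (poor responders leave) | 0.1m − 0.36 = −0.06 to +0.34 | 0.2m − 0.59 = +0.01 to +0.81 |

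With standard error 6.9·√(2/47) = 1.42, the noncentral t gives a two-sided type I error of 5.5% at a bias of 0.3, about 9% at 0.81 and 16.4% at 1.4. Simulating the baseline-scored data directly at 47 per arm gives 17.4% for the last case. At d_C = d_I = 10% the bias is zero for either ρ.

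**3. Bias under LOCF with the actual visit schedule.** Control leavers carry baseline. Intervention leavers may carry a share f of the month 6 gain from month 1 or month 3. With leaving unrelated to outcome and a true mean fall R in both arms,

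bias = R·[(1 − d_I) + d_I·f] − R·(1 − d_C) = R·[d_C − d_I·(1 − f)]

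For R = 6 and f = 0.5 (assumed), with control/intervention dropout of:
- 10%/10%: 6 × 0.05 = 0.30 points
- 20%/10%: 6 × 0.15 = 0.90 points
- 30%/10%: 6 × 0.25 = 1.50 points

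So even equal dropout gives some bias once interim gains are carried forward.

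**4. What following leavers would show.** If control leavers take up the care and gain a share s of the effect, the month 6 difference is 4.3·(1 − d_C·s). At 20% and s = 0.5 it is 3.87 points, with power 77% at 47 per arm. At 30% and s = 1 it is 3.01 points, with power 55%. With no take-up and all 47 per arm measured, power is 84.8%.

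**The case against.** The strongest reply is that the Protocol does prespecify a missing-data rule. With LOCF everyone randomised can be analysed as assigned, so a reader who infers that no intention-to-treat result can be obtained goes too far. What cannot be obtained is a comparison of observed month 6 outcomes in all randomised participants.

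A reader might also infer that leaving is rewarded in the control arm. The text says only that leavers are offered intervention-like or standard care. It does not say how soon, and nothing shown says participants learn of the offer at enrolment. The incentive is a plausible risk, not a documented fact.

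Nor do the documents support a large false harm from poor responders leaving. That would need leavers to be excluded from the analysis, which is not planned. With leavers scored at baseline, the same mechanism gives close to zero at the lower end. At equal 10% dropout with no interim gain carried, there is no bias at all. The unequal carrying of interim scores comes from the visit schedule combined with LOCF, and would remain even without the offer.

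Finally, the sample size text expects losses to follow-up and withdrawals of consent. If most dropouts are of those kinds, continued follow-up will recover little.

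These points limit the size and certainty of the problem. They do not answer the central one: the rule ends measurement even for leavers who are willing to answer, and does so on purpose.

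**Conclusion.** The concern holds in limited form. The rule on dropout conflicts with the intention-to-treat aim: an as-randomised result can be computed, but for leavers it is an imputation whose inputs differ by arm, and crossover by controls is unrecorded. On the stated assumptions with leavers scored at baseline, the bias is about -0.1 to +0.8 points if poor responders leave and +0.3 to +1.4 if leaving is unrelated to outcome, against a planned 4.3; type I error reaches about 16%. Carried interim gains in the intervention arm would add to this. Everything rests on assumed unequal dropout. The documents give only 10%, and equal dropout with no interim gain carried gives zero. This should be fixed. It is not fatal to the trial, but it cannot be repaired once follow-up has ended.

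**What to change.** - **Intervention Group, Control Group and Continuity of care plan:** limit the end of data collection before month 6 to withdrawal of consent to data or loss of contact. Send every other leaver the month 6 PHQ-9/GAD-7 six months after randomisation, by the existing link or by the in-person alternative in the Randomization section. Record whether and when intervention-like care was taken up.
- **Primary outcomes:** set the endpoint at month 6 after randomisation for everyone randomised.
- **Control Group and Continuity of care plan:** reconcile the offer made at dropout with the statement that controls receive no specific interventions for six months. Who may receive which care is for the trial team to decide.

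The cost is a protocol amendment, a sentence in the consent form and use of a questionnaire system already in place. The statistical price is dilution if control leavers take up the care: at 20-30% control dropout with half to full benefit, the difference falls from 4.3 to about 3.9-3.0 points, and power at 47 per arm to about 77-55%. The sponsor should weigh that against the sample size. It is, however, a dilution that can be seen and reported, whereas the bias under the present rule cannot be detected from the data.

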**Both Groups**

- Indication of medication (i.e. MDD, GAD, or both) will be recorded by the pharmacist partner in the secured study electronic website/database.
- The electronic PHQ-9/GAD-7 questionnaire (Appendix 4) will be sent securely to and completed by the participant at enrollment (month 0) and prior to the participant's in-person scheduled month 6 (final). The questionnaire results will be available to the study investigator and pharmacist participants but linked only to the participant's study ID.
- Participants will receive a pamphlet copy of Alberta Health Services Access Mental Health resource pamphlet "Know Your Addiction and Mental Health Options" which provides information regarding walk-in services, crisis support, and urgent care (10). An equivalent alternative pamphlet can be developed and provided by the study team if this document becomes obsolete or additional update/information is required.

**Continuity of care plan:**

- Should participants from either group drop out or complete the 6 month study period, they will be offered care similar to the interventional group or standard pharmacist care as outlined in the Alberta college of pharmacists standards of practice but no data will be collected since their dropout or study completion.

**Recording interventions:**

Intervention types will be documented by the pharmacist partner using the secured electronic study website/database. This electronic website/database will indicate the participants unique ID, their group assignment, the date of enrollment, current date of interaction. During these interactions (in-person/telehealth), the pharmacist partner will review the participant's PHQ-9/GAD-7 score and select the interventions performed.

The completed interactions will be recorded using the electronic study website/database. All inputs will be encrypted and stored at a central electronic database on University of Alberta servers for the investigational team to analyse at study completion.

---

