### **Randomization**

Multiple pharmacies are involved in participant enrollment--therefore, once informed written consent is obtained from the patient, the patients will be randomised by stratified randomization using a blocking factor to assign participants to either intervention or usual care groups.

Each participant will be assigned a unique identifier number and group allocation for the duration of their participation in the study--this unique identifier and allocation will also be communicated to and recorded by the pharmacy partner in the participant's patient profile to ensure consistency of the degree of pharmacist interventions described by the group the participant is allocated to.

The participant will be sent a secured electronic link (to the contact number or email they provided in the written consent form) that will include the participant's unique identifier and group allocation and the electronic version of the PHQ-9/GAD-7 questionnaire tool to complete and submit electronically. If the participant is unable to provide a means for the electronic link to be sent, the questionnaire tool can be completed with the pharmacist partner in person prior to their scheduled in-person/telehealth pharmacist meetings.

The study data (i.e. the participant's submitted electronic questionnaire tool results) will be sent directly to a centralised and secured website/database to ensure allocation concealment for the investigational team.

The participant questionnaire scores are available to the pharmacist partner via a secured electronic website/database prior to their scheduled in-person/telehealth meeting with the pharmacist partner.

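### The visible protocol gives no one a duty to read a control participant's month-0 PHQ-9 item 9 answer promptly

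*Protocol*

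**What the plan says.** The questionnaire in Appendix 4 includes PHQ-9 item 9, scored 0 to 3. Under Both Groups, the form is "completed by the participant at enrollment (month 0) and prior to the" month-6 visit.

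Under Randomization, the usual route is a secure link carrying the participant's "unique identifier and group allocation and the electronic version of the PHQ-9/GAD-7 questionnaire tool to complete and submit electronically". Because the link carries the allocation, it goes out after randomisation. Answers go straight to a central database. A participant who cannot receive a link may complete the form with the pharmacist.

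Access is described twice. Randomization says: "The participant questionnaire scores are available to the pharmacist partner via a secured electronic website/database prior to their scheduled in-person/telehealth meeting". Both Groups says: "The questionnaire results will be available to the study investigator and pharmacist participants but linked only to the" participant's study ID. The second statement does not tie access to a meeting.

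Review is described once for participants in general, under Recording interventions: "During these interactions (in-person/telehealth), the pharmacist partner will review the" participant's score and select what was done. The same section gives the investigational team's use of the data as analysis once the study is complete.

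The arms differ in what is scheduled. The intervention group has its listed components "at enrolment (month 0) and at the scheduled month 1, 3, and 6 in-person or telehealth pharmacist meetings", and the first is "Recording participant scores from the combined PHQ-9/GAD-7 questionnaire tool". Assessment of suicidal ideation, at the pharmacist's discretion, is in the same list. Controls receive standard pharmacist care and "physician care with no specific interventions for the duration of the 6 month study period".

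**The concern.** The trial asks people who are just starting treatment for depression or anxiety whether they have thoughts of death or self-harm. Having asked, it needs someone whose job is to see the answer soon. The protocol sets out how the form is delivered, stored, accessed and reviewed, and in the control arm that routing has a gap: being able to see a result is not a duty to look at it, and the stated review happens only when a pharmacist interaction takes place.

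This is a matter of participant safety, fixed by the protocol's own procedures, and would not normally be left to a statistical analysis plan. What is at stake is a missed warning in an individual, which may be irreversible.

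**Working it through.** No figure in the plan needs reproducing. The check sets the sections side by side and follows one positive month-0 answer through them.

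**Inputs**

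| Item | Intervention | Control | Protocol section |
|---|---|---|---|
| Questionnaire required in both arms | Months 0 and 6 | Months 0 and 6 | Both Groups |
| Arm-specific duty to record scores | Months 0, 1, 3, 6 (4 points) | None written | Intervention Group; Patient Assessment; Control Group |
| Next named study contact after enrolment | Month 1 | Month 6 | Intervention Group; Both Groups |
| General review of the score | During an interaction | During an interaction | Recording interventions |

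**Path of the answer**

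1. The participant consents, is randomised and receives the link. The pharmacist's clinical assessment described under Recruitment comes before this, so it cannot include the answer.
2. *Form completed at the enrolment contact.* The general review statement can apply at once, in either arm. There is no gap if the pharmacist looks.
3. *Form submitted by link after that contact.* The answer is in the database. Nothing in the visible text sends an alert or sets a time limit for reading it. Review waits for the next interaction.

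**Longest wait in case 3, if nobody looks earlier**

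- Control: 6 − 0 = 6 months.
- Intervention: 1 − 0 = 1 month. It is shorter if an interim call follows a treatment change.
- Difference: 6 − 1 = 5 months.

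**People exposed**

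The planned control group is 42 × 1.10 = 46.2, rounded up to 47 (Sample Size Calculation). The share with item 9 of 1 or more is not given, so the number of controls affected can only be bounded between 0 and 47. It should not be assumed small: the planning baseline PHQ-9 mean is 15.2, inside the protocol's moderately severe band of 15 to 19.

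**Does another safeguard close the gap?**

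- Exclusion criteria: severe depression and 2 or more suicide attempts per year are excluded. This lowers the risk, but a single recent attempt does not exclude.
- Recruitment: the physician is told of participation, not of item 9.
- Both Groups: the crisis-support pamphlet is information for the participant.
- Secondary outcomes: suicidal ideation is captured if the participant discloses it to the pharmacist.
- Sample Size Calculation: the monitoring board reviews adverse events, with data sent at 25% recruitment (24 participants).
- Competency and adherence: random audits check data entry and adherence to the protocol.
- Appendix 5: standard care may gather history of suicide attempts.

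Each helps, but none makes anyone read the month-0 answer.

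**The case against.** The strongest reply is that enrolment is itself a pharmacist contact. The form is due at enrolment in both arms, the review statement is not limited to one arm or to scheduled visits, and the pharmacist has just assessed and consented the patient. On that reading a control's month-0 answer is reviewed the same day. Controls also collect medication from the same pharmacy, remain under physician care, and can raise a concern at any time. The 6-month figure therefore needs three things together: submission after the contact, no one opening the available result, and no later interaction that prompts a look. Alert handling might also be covered in pharmacist training, the database build or pages not in the review copy.

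Much of this stands. A reader might infer that controls' answers will generally lie unread for six months, or that pharmacists are barred from looking at them. The documents support neither: completion and review at enrolment are allowed, and Both Groups gives access without tying it to a visit. What the reply does not supply is a duty. The usual link route permits later submission, and the visible text then names no one to read the answer and sets no time.

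It is also fair to object that the cost of an alert cannot be called slight. With any non-zero answer as the trigger and the positive share unknown, the number of extra contacts with controls is unknown, and those contacts could affect the PHQ-9 contrast.

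**Conclusion.** The point holds as a gap in assigned responsibility, and it should be fixed. In the visible protocol no one must promptly read a control's month-0 item 9 answer. If the form arrives by link after the enrolment contact, the next named study contact is month 6. The wait of up to about 6 months, against about 1 month in the intervention arm, is a worst case resting on the assumptions above, not an expected delay.

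Confidence is medium, because practice at enrolment may close much of the gap and removed pages may say more. A reader might also infer harm to the trial's power or bias in its estimate. Nothing in the documents supports that, and it is not claimed.

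**What to change.** Amend Randomization, Both Groups and Control Group as follows.

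- **At enrolment.** Where possible, the month-0 form is completed during the enrolment contact, and the pharmacist reads item 9 before the participant leaves.
- **Electronic submissions.** Any item 9 score of 1 or more (any answer other than the lowest category), in either arm and at every questionnaire, triggers a database alert to the pharmacist partner. The alert is acknowledged within one working day. If it is not, it goes to a back-up: a second pharmacist at the site, or the study coordinator at single-pharmacist sites.
- **Status of the response.** Responding to an alert under the existing standards of practice is standard care and not a protocol deviation. Routine review of total scores between visits remains part of the intervention.
- **Reporting.** Alerts and the contacts that follow are recorded by arm.

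The trigger and the one-working-day limit are proposals; the protocol gives no values for them. The build is one alert rule and a short amendment. The pharmacist already records the study ID in the patient's profile, so an alert can be matched to a person. Pharmacy Recruitment requires all staff pharmacists at a site to hold the same authorisations, so a second recipient needs no new staff where a site has more than one.

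The downside is extra safety contacts in up to 47 controls, number unknown, with some possible dilution of the contrast between arms. The record by arm lets this be reported. Because only item 9 triggers contact, the tested package of scheduled assessment and prescribing stays confined to the intervention arm.
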